14.3 Stratification Factors

Not applicable.

14.4 Analysis of Secondary Endpoints

The secondary endpoints of acute and late toxicity, tumor response, failure patterns and overall survival are defined in the modality review of 10.1-10.7. Toxicity and response data will be summarized in tables, with the exact binomial confidence interval reported for their rates. Time to failure and survival will be analyzed using standard methods for failure time data, primarily the Kaplan-Meier estimate, while differences between patient subgroups may be explored using the log-rank test. In particular, the increase in sample size will provide high precision for estimating the failure and survival endpoints separately for patients with hepatocellular cancer and cholangiocarcinoma.

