5.6 Duration of Follow Up

Study participants will be followed for five years from the completion of study treatment or until death, whichever occurs first. Participants will be removed from follow-up when any of the criteria listed in Section 5.5 apply. Participants removed from treatment or follow-up will be followed for survival outcomes and a 2 years analysis of local control.

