6. EXPECTED TOXICITIES AND DOSING DELAYS/DOSE MODIFICATIONS

6.1 Potential Toxicity

Radiation side effects are typically divided into those that occur acutely (during radiation and up to 3 months after radiation) and those that occur later (>3 months post-radiation). Common acute radiation side effects include fatigue, skin irritation or erythema, elevated liver function tests, nausea, low platelet count, decreased blood counts, abdominal pain or cramps, decreased/ loss of appetite, vomiting, slow wound healing, weight loss, indigestion, gastritis, radiation esophagitis, and diarrhea. Typically, these side effects can be controlled with medication.

Late side effects that are unlikely to occur but would include rib microfracture, nerve damage, inflammation and scarring of liver, mucosal ulceration and tissue damage, ulceration or perforation of stomach/ bowel, pain, inflammation, or scarring of kidneys, stomach and bowel, development of new cancer, hepatic injury (hepatitis), renal injury, gastric, bowel obstruction and spinal cord injury. Another rare but serious late side effect is the development of second tumors. It is hoped that proton radiation will substantially reduce both acute and late side effects by reducing the amount of normal tissue that is irradiated.

Dose delays and modifications will be made using the following recommendations. Toxicity assessments will be done using NCI Common Terminology Criteria for Adverse Events (CTCAE v3.0) which is available at <http://ctep.cancer.gov/reporting//ctc.html>).

If possible, symptoms should be managed symptomatically. In the case of toxicity, appropriate medical treatment should be used (including anti-emetics, anti-diarrheals, etc.).

All toxicities that are Grade 2 or higher and determined to be possibly, probably or definitely related to the study intervention or study procedures will be collected on the Toxicity case report forms from the time of the first dose of study treatment, through the study and until the final study visit. Participants continuing to experience toxicity at the off study visit may be contacted for additional assessments until the toxicity has resolved or is deemed irreversible.

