14.1 Study Design/Endpoints

The primary endpoint is local control at 2 years, or equivalently, the absence of local failure as defined in 10.3. Starting with a total of 60 patients with unresectable primary hepatocellular cancer, we project 30 of them will be alive at 2 years for the evaluation of local control assuming a 2-year overall survival of 50%. The number of evaluable patients is a conservative assumption based on the historical RFA data and the Tsukuba proton data (13) showing a 2-year overall survival in the range of 50-70%. Analysis of 30 patients alive at 2 years will achieve 94% power to detect a local control rate of 80% if at least 21 of them were free of local failure. The decision rule is associated with 7% probability for accepting the proton protocol is associated with improved local control when the true rate is only 55% at 2 years.

The rate of local control will be based on actuarial estimates, primarily at 2 years, using the Kaplan-Meier method. Time to local failure will be measured from the start of radiation therapy to the date of local failure, as defined in 10.3. Patients who have not failed locally will be censored at the time of last follow-up. A minimum follow-up of 2 years will be required, while patients who die or drop out of the protocol prior to 2 years will be censored at that date.

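### Late toxicity is planned only as a binomial rate with no time point or censoring rule, although toxicity follow-up can end before death or 5 years

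*Combined protocol and SAP*

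**What the plan says.** Section 14.4 counts late toxicity among the secondary endpoints: "The secondary endpoints of acute and late toxicity, tumor response, failure patterns and overall survival are defined in the modality review of 10.1-10.7". For acute and late toxicity alike the method is: "Toxicity and response data will be summarized in tables, with the exact binomial confidence interval reported for their rates". The following sentence keeps failure-time methods for other endpoints: "Time to failure and survival will be analyzed using standard methods for failure time data, primarily the Kaplan-Meier estimate". Section 14.5, on reporting and exclusions, is marked as not applicable.

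Section 6.1 defines late effects as "those that occur later (>3 months post-radiation"). The study calendar (9.1, 9.2) schedules toxicity assessment at 1 month and then at intervals to 60 months.

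Three sections bear on how long a patient is observed for toxicity:

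- Section 5.6 opens with "Study participants will be followed for five years from the completion of study treatment or until death, whichever occurs first". It then takes patients out of follow-up when a 5.5 criterion applies. Those criteria include disease progression and withdrawal. For removed patients it names only survival and the 2-year local control analysis as continuing.
- Section 6.1 collects related toxicity of Grade 2 or higher up to the final study visit.
- Section 11.1 describes adverse event collection from the start of the intervention, through the study, and within 30 days of the last treatment. Events still ongoing at that point are followed further.

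Section 14.1 foresees patients who die or drop out before 2 years and censors them, but only for local control.

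**The concern.** A binomial proportion estimates a defined risk when each patient is observed either to a common horizon or to death. Acute toxicity, confined to treatment and the 3 months after it, is close to that. Late toxicity is not. A patient whose toxicity assessments stop at progression in month 8 has had little chance to show a late event. If that patient stays in the denominator, he or she counts as free of late injury. Section 14.4 does not state the denominator, but it offers no other way to handle such a patient.

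Safety and tolerance is the first secondary objective (1.3.1). Under the stated method late injury looks rarer the more follow-up is lost. A rate with no time attached is also hard to set beside another series, or to compare between the hepatocellular and cholangiocarcinoma groups if their loss differs.

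**Working it through.** **The plan's own figures.** The plan gives no expected late-toxicity rate and no precision for one, so there is no toxicity figure to reproduce. The figure used here is survival in the hepatocellular group: "we project 30 of them will be alive at 2 years for the evaluation of local control assuming a 2-year overall survival of 50" per cent. This checks: 60 × 0.50 = 30. Section 14.1 calls it conservative and cites data "showing a 2-year overall survival in the range of 50-70" per cent.

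**Inputs**

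- From the documents: 2-year survival 50% (14.1), late period from 3 months, that is 0.25 years (6.1), horizon 5 years (5.6).
- Assumed: 20% net risk of a late event by 5 years, that is, the risk if nobody died; loss of toxicity follow-up at 0, 0.1 or 0.2 per year; constant hazards; loss independent of toxicity; one time origin for survival and toxicity.

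**Hazards per year**

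- Death: d = ln 2 / 2 = 0.3466.
- Late event, from 0.25 years: h = −ln(0.8) / 4.75 = 0.04698.
- Loss: c = 0, 0.1 or 0.2.

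**Proportion of all patients with a late event observed by 5 years**

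P(c) = exp(−(d + c) × 0.25) × h/(h + d + c) × [1 − exp(−(h + d + c) × 4.75)]

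| Yearly loss c | First term | Second term | Third term | P(c) | Relative to c = 0 |
|---|---|---|---|---|---|
| 0 | 0.9170 | 0.1194 | 0.8458 | 9.3% | 1.00 |
| 0.1 | 0.8944 | 0.0952 | 0.9041 | 7.7% | 0.83 |
| 0.2 | 0.8723 | 0.0791 | 0.9404 | 6.5% | 0.70 |

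The row c = 0 is the cumulative incidence with death as a competing event. With death as the only loss, the crude proportion equals it, so death contributes no bias. The shortfall of 17% or 30% in relative terms comes entirely from loss.

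**Sensitivity to survival.** At 70% survival at 2 years, d = −ln(0.7)/2 = 0.1783. The same formula gives 13.1%, 10.6% and 8.7%, that is 19% and 33% low. The result does not hang on the 50% figure.

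**A 2-year horizon.** Take 20% net risk by 2 years, 50% survival, and 10%, 30% or 50% removed from toxicity follow-up by 2 years. The crude rate is 13.2%, 11.7% or 10.0% against a cumulative incidence of 13.9%, or about 5%, 16% and 28% low.

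**The interval.** In 8,000 simulated trials per setting at 2 years, with 50% survival, 10% or 20% net risk and no loss other than death, the exact 95% interval covered the cumulative incidence 97–98% of the time for 60 and for 90 patients. With 20% net risk, 50% removed and 90 patients, coverage fell to 89%, and to 84% at 70% survival. The interval fails only when loss is heavy.

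**The case against.** The strongest reply is that exact binomial tables are a conventional description of toxicity in a single-arm phase II trial, and that late toxicity is not tested. The plan intends 5 years of follow-up or death for everyone, and section 5.7 removes patients from the study only at death or withdrawal of consent. If toxicity is in fact assessed throughout, the crude rate is sound. The absolute gap in the illustration is 1.6 to 2.8 percentage points, which is small beside the sampling error: the exact 95% interval is 3.2–15.4% for 7 of 90 and 2.5–13.9% for 6 of 90, and both contain 9.3%.

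Much of this stands. The size is unknown and could be small. However, section 5.6 does end follow-up at the 5.5 criteria and does not list toxicity among what continues, so complete toxicity observation cannot be assumed. Wide intervals do not excuse an estimate that moves with the amount of loss.

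Three stronger readings are tempting, and the documents do not support them.

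- A reader might infer that late injury is understated because half the patients are expected to die. The c = 0 row shows otherwise. The crude rate is lower than the risk in a population where nobody dies, but that is a different quantity. The 50% is also a planning value for hepatocellular cancer only.
- A reader might infer that the exact interval is simply wrong. It is valid when death is the only loss.
- A reader might add bias from staggered entry. Spreading follow-up evenly over 2 to 5 years would also give 7.7% against 9.3%. But nothing says late toxicity is analysed at a 2-year cut, and an even spread does not match the accrual in 14.2 (47 patients over 13 months, 57 by March 2013). Section 14.1 requires at least 2 years of follow-up, so staggering would not bias a 2-year rate.

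**Conclusion.** The point holds for loss of toxicity follow-up before death or 5 years, and only for that. Section 14.4 applies to late toxicity a method that has no time point and no way to handle such loss, while 5.5, 5.6 and 14.1 foresee it. The direction is clear if lost patients stay in the denominator: the late rate is too low. The size is illustrative, at 17% to 30% in relative terms at 5 years for 10% to 20% yearly loss, and about 5% at 2 years if only 10% are removed by then. These figures rest on assumed event and loss rates, constant hazards and independent loss. Removal at progression may well be related to the patient's liver condition, and the size and direction of that effect cannot be worked out from the documents. This concerns a secondary safety endpoint. The primary test of local control does not change.

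**What to change.** In 14.4:

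- Keep tabulated rates with exact binomial intervals for acute toxicity.
- For late toxicity, report the cumulative incidence at 1, 2 and 5 years with death as a competing event, censoring at the last toxicity assessment, with 95% intervals and numbers at risk, overall and by histology. State the time origin.

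Reconcile 5.5/5.6 (when follow-up ends and what continues), 6.1 (toxicity to the final study visit) and 11.1 (adverse events within 30 days of the last treatment) on how long toxicity is collected, and in particular whether it continues after removal from follow-up. If collection really stopped at 30 days, new events after 3 months could not be captured and no analysis method would recover them. If it stops at progression, the report should say so, because the competing-risk estimate still assumes that censored patients resemble those who remain.

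The cost is one or two sentences in 14.4 and a standard procedure. Each late event also needs a recorded onset date, or the date of the assessment that first showed it. The protocol describes toxicity forms and visits but does not say that onset dates are collected, so this should be checked. The reported late rates may be somewhat higher, with wider intervals.

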Given these promising results in otherwise incurable malignancies, the MGH group undertook a Phase I study to evaluate the use of high dose conformal proton beam irradiation for selected patients with hepatocellular cancer, cholangiocarcinoma and hepatic metastases. The dose escalation was based on a model based on the amount of radiation that the normal liver received, or equivalent uniform dose (EUD) to the liver. The eligibility criteria were 1-3 lesions, greatest less than 6 cm in size, Childs A/B, and no extrahepatic disease. Patients were treated with gated proton beam therapy using 4D treatment planning techniques. Generally, patients have been treated to a dose of 45-75 Gy (RBE) in 15 fractions. The study was a dose escalation trial based on liver EUD. The dose that each patient was treated to was based not only on the liver EUD at each step but had to comply with protocol defined normal tissue constraints (bowel, chest wall). To date, there have been no local failures or radiation-induced liver disease through 3 of the first 4 dose levels.

CONFIDENTIAL

This document is confidential. Do not disclose or use except as authorized.

Because of the limitations of the EUD based liver concept as a dose escalation platform, as well as the non dose-limiting nature of liver with proton therapy, we have decided to proceed with a modification of the approach taken by the Tsukuba group (13). Investigators at Tsukuba have treated 165 patients (192 tumors) with a similar 15 fraction protocol to a median dose of 72 Gy. Patients with tumor sizes of 10 cm or greater were allowed on the study. Central tumors (within 2 cm of the porta hepatis) were treated to 66 Gy in 22 fractions because of concerns of toxicity. Local control at 5 years was an impressive 86.9%. Local control at 2 years was 90%. However 5 yr OS was only 23%, highlighting the out of field progression and comorbidities in these patients. In this study, we propose a treatment schedule of 15 fractions of proton beam radiation with an expected 2 yr LC of > 85%. Because we anticipate treating large tumors generally greater than 3 cm, we will seek to improve upon a RFA local control rate of ~ 50% to 80% with proton beam therapy.

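### One minus Kaplan-Meier with deaths censored will overstate the proportion of patients who fail at each site; section 14.4 should add cumulative incidence

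*Combined protocol and SAP*

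**What the plan says.** Section 14.4 lists failure patterns among the secondary endpoints and states that "Time to failure and survival will be analyzed using standard methods for failure time data, primarily the Kaplan-Meier estimate". It names no competing-risk method; subgroups may be explored by log-rank test.

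Sections 10.3 to 10.6 define local, marginal, nodal and distant failure as tumour events. Death belongs to none of them.

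For time to local failure, 14.1 is explicit: "Patients who have not failed locally will be censored at the time of last follow-up", and "patients who die or drop out of the protocol prior to 2 years will be censored at that date".

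On mortality, 14.1 starts from 60 hepatocellular patients: "we project 30 of them will be alive at 2 years for the evaluation of local control assuming a 2-year overall survival of 50" per cent. It calls this conservative within a cited range of 50 to 70%. For the earlier proton series, section 2.3 reports: "However 5 yr OS was only 23%, highlighting the out of field progression and comorbidities in these patients".

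Patterns of failure are a secondary objective for hepatocellular cancer (1.3.2) and cholangiocarcinoma (1.3.4). Section 14.2 continues cholangiocarcinoma accrual so that its failure and survival endpoints can inform later studies.

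**The concern.** A patient who dies without failure at a given site can no longer fail there. Censoring that death treats the patient as still at risk and, in effect, gives the patient the later failure experience of those who survive. One minus Kaplan-Meier then estimates net failure, meaning failure in a setting where nobody dies first, and does so only if death is independent of failure. It does not estimate the share of treated patients in whom the failure occurs.

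With 30 to 50% of patients projected to be dead by 2 years, the two quantities differ visibly. Section 2.3 also reports that in earlier conformal photon series most deaths came from underlying cirrhosis rather than from tumour or treatment, so deaths without failure may be common. At stake is the descriptive result on patterns of failure: someone planning a later trial needs the proportion of patients who fail at each site, and the planned method gives a larger number.

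**Working it through.** **Step 1: the plan's own figures.** 60 × 0.50 = 30 evaluable patients. For at least 21 of 30 free of local failure, the exact binomial probability is 0.0694 at a true rate of 55% and 0.9389 at 80%. The plan's 7% and 94% reproduce, and nothing below changes them.

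**Step 2: direction.** At each failure time, one minus Kaplan-Meier grows by (net probability of no failure so far) × (failure hazard). Cumulative incidence grows by (probability of being alive and failure-free so far) × (the same hazard). The second probability is never larger than the first, so one minus Kaplan-Meier is never below the cumulative incidence.

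**Step 3: size.** Assume constant, independent hazards. Let N be one minus Kaplan-Meier at the time point, S overall survival at that point, and a the share of the death hazard that is failure-free. Then

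- F = −ln(1 − N)
- D = −a × ln(S)
- cumulative incidence = F/(F + D) × (1 − exp(−(F + D)))

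Inputs: N = 20% at 2 years is the complement of the 80% target (1.2, 14). S = 50% and 70% come from 14.1. S = 23% and N = 13.1% at 5 years (100 − 86.9) come from the earlier proton series in 2.3; that the 86.9% is a Kaplan-Meier figure is assumed. N = 20% at 5 years and a = 0.5 are assumptions. For N = 20%, F = 0.2231; for N = 13.1%, F = 0.1404.

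| Time | S | a | N | D | Cumulative incidence |
|---|---|---|---|---|---|
| 2 y | 50% | 1 | 20% | 0.6931 | 0.2435 × 0.600 = 14.6% |
| 2 y | 70% | 1 | 20% | 0.3567 | 0.3849 × 0.440 = 16.9% |
| 2 y | 50% | 0.5 | 20% | 0.3466 | 0.3917 × 0.434 = 17.0% |
| 5 y | 23% | 1 | 20% | 1.4697 | 0.1318 × 0.816 = 10.8% |
| 5 y | 23% | 0.5 | 20% | 0.7348 | 0.2329 × 0.616 = 14.4% |
| 5 y | 23% | 1 | 13.1% | 1.4697 | 0.0872 × 0.800 = 7.0% |
| 5 y | 23% | 0.5 | 13.1% | 0.7348 | 0.1604 × 0.583 = 9.4% |

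In the first row, 60 hepatocellular patients would give 60 × 0.146 = 8.8 local failures by 2 years, where the Kaplan-Meier figure suggests 60 × 0.20 = 12.

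**Step 4: check by simulation.** With 60 patients, 3,000 runs, net failure 20% and survival 50% at 2 years, the mean of one minus Kaplan-Meier was 20.1% and the mean Aalen-Johansen estimate 14.6%, with standard deviations of 6.2 and 4.6 points.

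**The case against.** **The text is less definite than the criticism.** Section 14.4 does not say that deaths are censored for every failure type, and its wording leaves room for other methods, including plain tabulation of failure sites. Censoring of deaths is written out only for local failure. This stands as a caveat. But the endpoint definitions exclude death, so a Kaplan-Meier curve for any of them has to censor it, and no alternative is specified.

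**Kaplan-Meier is legitimate for local control.** This stands in full. A reader might infer that the primary analysis, or the 5-year local control aim, uses the wrong estimator. The documents do not support that: 14.1 defines local control as an actuarial quantity to be set against a benchmark, and a net estimate serves that purpose. The fault lies only in reading its complement as the proportion of patients who fail.

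**Rates adding to more than 100%.** A reader might count this as a further fault that per-site cumulative incidence would cure. It would not. Sections 10.3 to 10.6 do not make the sites mutually exclusive, so one patient may fail at several, and per-site incidences with only death competing can also sum above 100%.

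**The sizes are upper-end.** This stands where a = 1, because every death is then treated as failure-free. Also, 50% survival is a conservative planning value for hepatocellular cancer, 14.2 regards cholangiocarcinoma as having the better prognosis, and 23% belongs to an earlier series. The 2-year gap of 3 to 5 points is smaller than the simulated Kaplan-Meier standard deviation of 6.2 points. That limits its practical weight, but the gap is systematic and always in the same direction.

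**Follow-up ends at progression.** Under 5.5 and 5.6, a patient who progresses leaves ordinary follow-up and is then followed for survival and the 2-year local control analysis. Later failure at a second site may go unseen, and changing the estimator alone does not repair that. This stands and shapes the fix.

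**Conclusion.** The point holds for the proportion of patients who fail, and only for that. Following 14.4 as written overstates this proportion at each failure site. The direction does not depend on the assumed hazards; the size does. For a 20% Kaplan-Meier local failure at 2 years, the overstatement is 5.4 points at 50% survival and 3.1 points at 70% if all deaths are failure-free, and about 3 points at 50% survival if half the death hazard is. At 5 years with 23% survival, an assumed 20% is overstated by roughly 6 to 9 points.

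These figures rest on constant, independent hazards and on planning or historical survival, not on data from this trial. The primary hypothesis, the sample size and the 21-of-30 rule are unaffected. The change is worth making because the failure results are meant to inform later trials.

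**What to change.** In 14.4:

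1. Keep Kaplan-Meier for overall survival and for net local control, including the benchmark comparison and the 5-year local control aim.
2. Report by histology the Aalen-Johansen cumulative incidence of local failure, with death without local failure as the competing event, beside the Kaplan-Meier estimate.
3. Report by histology the cumulative incidence of first failure by site (local, marginal, nodal, distant), with first failure at the other sites and death without failure as competing events. First failure is the appropriate event because ordinary follow-up ends at progression. State how failures found at the same assessment are classified, and where new liver lesions away from the treated tumour (10.3) are counted.

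No new data are needed: the dates of death and of first failure follow from assessments already planned. The cost is a few sentences in 14.4 and a modest amount of analysis. The downside is that two local failure figures will stand side by side and the report must explain that one is net and the other is the proportion of patients who fail.
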